- 7 Morphology and WBC differential /blast count on aspirate. In general, bone marrow aspirates and biopsies will be performed at the end of C1 and C4 and then every 12 weeks (± 7 days) thereafter. Bone marrow evaluation should also be performed at End of Treatment; if a bone marrow evaluation was performed within 4 weeks prior to the end of treatment, a repeat evaluation does not need to be performed at this time, unless clinically indicated.
- 8 Bone marrow aspirate and imaging studies are to be repeated at the end of C1 and C4 and then every 12 weeks (± 7 days) thereafter.
- 9 Imaging studies will be performed at the end of C1 and C4 and then every 12 weeks (± 7 days) until there is evidence of relapsed or progressive disease. Abdominal scan is required; evaluation of chest/pelvis may be obtained at the Investigator's discretion. Scan must include measurement of spleen and liver volume. Imaging studies should also be performed at End of Treatment; if imaging was performed within 4 weeks prior to the end of treatment, a repeat evaluation does not need to be performed at this time, unless clinically indicated. Whenever clinically feasible, it is strongly requested that the same imaging modality (MRI or CT) at both baseline and subsequent timepoints be utilized for any given patient throughout their evaluation on-study.
- 10 Peripheral blood (serum) samples (10 mL) will be collected for the detection of tagraxofusp reactive antibodies at the completion of every cycle and at specified points thereafter.
- 11 Patients will be followed for survival approximately every 90 days, until assessment of the primary objective for the study is complete for all treated patients; please consult the appropriate protocol section for description of situations in which survival and other data may be collected following study completion. Patients who undergo SCT will be followed for the occurrence of veno-occlusive disease as part of long-term follow-up. A blood sample for immunogenicity studies will be collected at least 16 weeks to up to 20 weeks after the last tagraxofusp dose.
- 12 Premedications administered 60 minutes (± 15 minutes) before tagraxofusp treatment: Diphenhydramine 50 mg IV (or an equivalent dose of another H1-histamine antagonist); acetaminophen 650 mg orally (or equivalent dose of paracetamol); methylprednisolone 50 mg IV (or an equivalent dose of another corticosteroid); famotidine 20 mg IV (or an equivalent doses of another H2-histamine antagonist).
- 13 Following treatment with premedication, tagraxofusp will be administered as a 15-minute infusion once daily for the first 3 consecutive days of a 28-day cycle. Individual tagraxofusp infusions may be delayed to allow for toxicity resolution, but all 3 infusions should be completed within 10 days.
- 14 Patients should complete the MPN-SAF TSS (10-question evaluation concerning symptoms/well-being during the prior week) with every treatment cycle, prior to receiving therapy on the subsequent cycle. The MPN-SAF TSS should also be completed at End of Treatment.
- 15 Tumor response assessments are to be conducted every 12 weeks (± 7 days) and at End of Treatment, detailed in [Section 11.12](#), and [Section 18.1](#).

11 Study Procedures

11.1 Patient Selection

Patients with CMML who meet the inclusion/exclusion criteria will be recruited for enrollment into the study. Patients will be advised of the clinical protocol by the Investigator. If the patient is interested and is potentially eligible for participation in the study, he/she will be provided with the informed consent form (ICF) to review and sign. The ICF includes a detailed explanation of the study design and the potential risks and benefits of treatment. Patients who agree to participate in the study will be provided with a copy of the signed consent form; the original signed consent document will be filed in the patient's medical record. Only eligible and consenting patients will be entered into the study. No study procedures will be performed until the patient's written informed consent is obtained.

Patients will be screened by the Investigator or study nurse/coordinator prior to study entry. All patients enrolled on the study will be entered into a patient registration log at each site. Each screened patient will be assigned a sequential patient/study identification number with digits indicating site number and patient study number (e.g., XX-YYY, where XX denotes site number and YYY denotes patient study number as assigned at screening). Original screening records and source documents should be kept for all patients, including those who fail to meet the study eligibility requirements and any completed eCRFs should be retained for monitoring and auditing. Each patient's data obtained from subsequent evaluations should be recorded and evaluated in the source documents and eCRF. Prior to treatment, the Investigator will re-confirm patient eligibility criteria and assignment of the correct patient study number.

11.2 Medical History

Medical history includes current and past medical conditions and smoking history, date of MPN diagnosis, history of infections related to primary disease, prior treatment, response to prior treatment, and date of relapse, if applicable. Information concerning any prior malignancy diagnoses with particular focus on cytotoxic therapies received for prior malignancies (e.g., dates/duration of anthracycline for prior breast cancer) is to be collected whenever feasible.

11.3 Prior and Concomitant Medication

Medications taken within 28 days prior to the first study drug dose and throughout the study are to be collected and recorded. For patients with CMML, all transfusions (pRBC and platelets) within 8 weeks prior to the first tagraxofusp dose also are to be recorded. For patients with MF, all transfusions (pRBC and platelets) within 12 weeks prior to the first tagraxofusp dose are to be recorded.

11.4 ECOG Performance Status

See Section 18.2 for the ECOG-PS scoring guide.

11.5 Physical Examination

Physical examination includes evaluation by body system, weight, and height (screening only) performed at screening, and at subsequent time points as indicated in the applicable Schedules of Events ([Table 2](#) and [Table 3](#) for Stage 2; [Table 4](#) and [Table 5](#) for Stage 3A). Note that physical examination includes assessment for hepatomegaly and splenomegaly by palpation, with findings records as centimeters below the right costal margin and left costal margin, respectively. Of note, a spleen response by palpation must be confirmed by imaging studies to show reduction in spleen volume (or liver volume in splenectomized patients; refer to the response criteria outlined in [Appendix 18](#)).

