End of Treatment including patients who discontinue study therapy prior to completion of C4; if a bone marrow evaluation was performed within 4 weeks prior to the end of treatment, a repeat evaluation does not need to be performed at this time, unless clinically indicated.

- 11 Bone marrow aspirate and imaging studies are to be repeated at the end of C1 and C4 and then every 12 weeks (± 7 days) thereafter.
- 12 A baseline MRI or CT scan must be performed within 28 days prior to the first administration of tagraxofusp. Subsequent imaging studies will be performed at the end of C1 and C4 and then every 12 weeks (± 7 days) until there is evidence of relapsed or progressive disease. Abdominal scan is required; evaluation of chest/pelvis may be obtained at the Investigator's discretion. Scan must include measurement of spleen and liver volume. Subsequent to Week 24, for patients receiving ongoing therapy (or those who discontinue therapy but are without evidence of PD and continue to be evaluated in ongoing follow-up) the frequency of imaging studies may be reduced (obtained less frequently) if peripheral blood and/or clinical assessments indicate clinical stability, as per the Investigator's discretion, in consultation with the Medical Monitor. Imaging should also be performed at End of Treatment, including patients who discontinue study therapy prior to completion of C4; if a imaging was performed within 4 weeks prior to the end of treatment, a repeat evaluation does not need to be performed at this time, unless clinically indicated. Whenever clinically feasible, it is strongly requested that the same imaging modality (MRI or CT) at both baseline and subsequent timepoints be utilized for any given patient throughout their evaluation on-study.
- 13 Peripheral blood (serum) samples (10 mL) will be collected for the detection of tagraxofusp reactive antibodies on Day 1 (pre-infusion) and Day 21 (the end of cycle collection may also serve as the pre-infusion collection for the subsequent cycle).
- 14 Premedications administered 60 minutes (± 15 minutes) before tagraxofusp treatment: Diphenhydramine 50 mg IV (or an equivalent dose of another H₁-histamine antagonist); acetaminophen 650 mg orally (or equivalent dose of paracetamol); methylprednisolone 50 mg IV (or an equivalent dose of another corticosteroid); famotidine 20 mg IV (or an equivalent dose of another H₂-histamine antagonist).

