18.1 Disease-specific Response Criteria

Table 6: Stage 2: Revised IWG-MRT and ELN Response Criteria for MF

Response categories	Required criteria (for all response categories, benefit must last for ≥ 12 weeks to qualify as a response)
CR	
Bone marrow¹: Age-adjusted normocellularity; < 5% blasts; \leq Grade 1 MF² and
 
Peripheral blood: Hemoglobin ≥ 100 g/L and < ULN; neutrophil count $\geq 1 \times 10^9$/L and < ULN; Platelet count $\geq 100 \times 10^9$/L and < ULN; < 2% immature myeloid cells³ and
 
Clinical: Resolution of disease symptoms; spleen and liver not palpable; no evidence of EMH

PR	
Peripheral blood: Hemoglobin ≥ 100 g/L and < ULN; neutrophil count $\geq 1 \times 10^9$/L and < ULN; Platelet count $\geq 100 \times 10^9$/L and < ULN; < 2% immature myeloid cells³ and
 
Clinical: Resolution of disease symptoms; spleen and liver not palpable; no evidence of EMH
 
or
 
Bone marrow¹: Age-adjusted normocellularity; < 5% blasts; \leq Grade 1 MF² and
 
Peripheral blood: Hemoglobin ≥ 85 g/L but < 100 g/L and < ULN; neutrophil count $\geq 1 \times 10^9$/L and < ULN; platelet count $\geq 50 \times 10^9$/L but < 100×10^9/L and < ULN; < 2% immature myeloid cells³ and
 
Clinical: Resolution of disease symptoms; spleen and liver not palpable; no evidence of EMH

Clinical improvement (CI)	The achievement of anemia, spleen or symptom response without progressive disease or increase in severity of anemia, thrombocytopenia or neutropenia ⁴
Anemia response	Transfusion independent patients: a ≥ 20 g/L increase in hemoglobin level ⁵ Transfusion dependent patients: becoming transfusion independent ⁶
Spleen response⁷	
A baseline splenomegaly that is palpable 5-10cm below the LCM, becomes not palpable⁸ or
 
A baseline splenomegaly that is palpable > 10cm below the LCM, decreases by $\geq 50\%$⁸
 
A baseline splenomegaly that is palpable < 5cm below the LCM is not eligible for spleen response
 
A spleen response requires confirmation by MRI or CT showing $\geq 35\%$ spleen volume reduction

Symptom response	A $\geq 50\%$ reduction in the MPN-SAF TSS ⁹

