Criteria for measurement of treatment response in adult MDS/MPN

Clinical benefit

Requires 1 of the following in the absence of progression or CR/partial response and independent of marrow response (response must be verified at ≥ 8 weeks) to be considered a clinical benefit. (Note: “Cord blood response” was corrected to “response”.)

- Erythroid response
 - Hgb increase by ≥ 2.0 g/dL
 - Transfusion independence for ≥ 8 weeks for patients requiring at least 4 packed red blood cell transfusions in the previous 8 weeks
 - Only red blood cell transfusions given based on physician’s judgement for a pretreatment Hgb of ≤ 8.5 g/dL will count in the red blood cell TI response evaluation⁵
- Platelet response
 - Transfusion independence when previously requiring platelet transfusions of at least a rate of 4 platelet transfusions in the previous 8 weeks
 - Pretreatment $\leq 20 \times 10^9/L$: increase from $< 20 \times 10^9/L$ to $> 20 \times 10^9/L$ and by at least 100%
 - Pretreatment $> 20 \times 10^9/L$ but $\leq 100 \times 10^9/L$: absolute increase of $\geq 30 \times 10^9/L^5$
- Neutrophil response
 - Pretreatment $\leq 0.5 \times 10^9/L$, at least 100% increase and an absolute increase $\geq 0.5 \times 10^9/L$
 - Pretreatment, $> 0.5 \times 10^9/L$ and $\leq 1.0 \times 10^9/L$, at least 50% increase and an absolute increase $\geq 0.5 \times 10^9/L^5$
- Spleen response
 - Either a minimum 50% reduction in palpable splenomegaly of a spleen that is at least 10 cm at baseline or a spleen that is palpable at more than 5 cm at baseline becomes not palpable
- Symptom response (improvement in symptoms as noted by decrease of $\geq 50\%$ as per the MPN-SAF TSS scoring < 20 were not considered eligible for measuring clinical benefit)⁶

- 1 Presence of dysplastic changes, which may be interpreted within the scope of normal range of dysplastic changes, may still exist in the presence of CR as allowed in MDS IWG. Marrow should exhibit age-adjusted normocellularity in CR.
- 2 If there is no significant fibrosis present on the initial bone marrow biopsy, a second biopsy is not required to prove resolution of fibrosis. Grading of fibrosis in measurement of treatment response should be according to the European Consensus System (Thiele 2005).

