4.3.1. Response Rate

Objective response rate and the corresponding 95% Clopper Exact CIs will be presented as the number and percentage of patients who achieve disease-specific complete response (CR) or partial response (PR) after treatment.

Best overall response will be presented as the number and percentage of patients who achieve disease-specific (see [Section 8](#)) CR, PR, stable disease (SD), progressive disease (PD) or who are not evaluable (NE) as their best response on study.

Swim lane plots will be produced for each disease presenting the time on treatment and in response.

The time from the date of first infusion of tagraxofusp to the date from when criteria are first met for CR or PR will be summarized.

Patients who remain in response per investigator and receive a stem cell transplant will be identified and summarized.

For MF patients, the number and percentage of patients who achieved clinical improvement, anemia, spleen, or symptom responses, molecular remission, or cytogenetic/molecular relapse will also be presented using IWG-MRT/ELN criteria (see [Section 8.1](#) for disease specific response criteria). The time from date of first infusion of tagraxofusp to the date from when each response of clinical benefit criteria (as defined in Table 8-4 in [Section 8.2](#)) are first met will be summarized.

For CMML patients, the number and percentage of patients who achieved erythroid, platelet, neutrophil, spleen or symptoms responses will also be presented (see [Section 8.2](#) for disease specific response criteria). The time from date of first infusion of tagraxofusp to the date from when each category of clinical benefit criteria are first met will be summarized.

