4.3.2. Duration of Response

Duration of objective response is defined as the time from when the disease specific criteria (see [Section 8](#)) are first met for CR or PR until the date that the criteria for relapse (including SD, progressive disease [PD], or relapse) after CR/PR is met, or death. In the case that SD follows CR/PR and there is no evidence that response rebounds to CR/PR, duration of objective response will end at the time of first reduction of response to below CR/PR. For patients who receive SCT after CR/PR, DOR will include time to disease relapse post-transplant. Patients who are lost to follow-up or who do not relapse after objective response as of the analysis date will be censored on the latter of the date of last treatment with tagraxofusp or date of last disease

assessment recorded prior to the analysis date. If patient starts other anticancer therapies (with the exception of SCT), they will be censored at the latter of the date of last treatment with tagraxofusp or date of last disease assessment recorded that occurred prior to the start of the new therapy.

The distribution of DOR will be estimated by Kaplan-Meier methodology and the 25th percentile, median, and 75th percentile of time to event, number and percentage of events and censored observations, and appropriate 95% CIs will be presented.

For MF patients, the median duration of response for each category of clinical benefit, including clinical improvement, anemia, spleen, or symptom responses, molecular remission, or cytogenetic/molecular relapse, will be derived similar to the duration of objective response. For CMML patients, the median duration of response for each category of clinical benefit, including erythroid, platelet, neutrophil, spleen or symptoms responses, will be derived similar to the duration of objective response.

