4.3.5. Spleen Volume

Spleen size by MRI/CT will be summarized over time for all patients with baseline splenomegaly. The number and percentage of patients with $\geq 10\%$, $\geq 25\%$, and $\geq 35\%$ reduction in spleen volume from baseline will be summarized over time.

The maximum percent reduction from baseline in spleen size across all post-baseline visits will be summarized. A waterfall plot of the maximum percent reduction in spleen volume, spleen volume at Cycle 4 Day 21 visit, and spleen volume at Cycle 7 Day 28 will be created.

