- Normalization of peripheral counts and hepatosplenomegaly with bone marrow blasts (and blast equivalents) reduced by 50%, but remaining > 5% of cellularity except in cases of MDS/MPN with $\leq 5\%$ bone marrow blasts at baseline

Marrow response

- Optimal marrow response: Presence of all marrow criteria necessary for CR without normalization of peripheral blood indices as presented above
- Partial marrow response: Bone marrow blasts (and blast equivalents) reduced by 50%, but remaining > 5% of cellularity, or reduction in grading of reticulin fibrosis from baseline on at least 2 bone marrow evaluations spaced at least 2 months apart

Clinical benefit

Requires 1 of the following in the absence of progression or CR/partial response and independent of marrow response (response must be verified at ≥ 8 weeks) to be considered a clinical benefit. (Note: “Cord blood response” was corrected to “response”.)

- Erythroid response
 - Hgb increase by ≥ 2.0 g/dL
 - Transfusion independence for ≥ 8 weeks for patients requiring at least 4 packed red blood cell transfusions in the previous 8 weeks
 - Only red blood cell transfusions given based on physician’s judgement for a pretreatment Hgb of ≤ 8.5 g/dL will count in the red blood cell TI response evaluation⁵
- Platelet response
 - Transfusion independence when previously requiring platelet transfusions of at least a rate of 4 platelet transfusions in the previous 8 weeks
 - Pretreatment $\leq 20 \times 10^9/L$: increase from $< 20 \times 10^9/L$ to $> 20 \times 10^9/L$ and by at least 100%
 - Pretreatment $> 20 \times 10^9/L$ but $\leq 100 \times 10^9/L$: absolute increase of $\geq 30 \times 10^9/L$ ⁵
- Neutrophil response
 - Pretreatment $\leq 0.5 \times 10^9/L$, at least 100% increase and an absolute increase $\geq 0.5 \times 10^9/L$
 - Pretreatment, $> 0.5 \times 10^9/L$ and $\leq 1.0 \times 10^9/L$, at least 50% increase and an absolute increase $\geq 0.5 \times 10^9/L$ ⁵
- Spleen response
 - Either a minimum 50% reduction in palpable splenomegaly of a spleen that is at least 10 cm at baseline or a spleen that is palpable at more than 5 cm at baseline becomes not palpable

Symptom response (improvement in symptoms as noted by decrease of $\geq 50\%$ as per the MPN-SAF TSSscoring < 20 were not considered eligible for measuring clinical benefit)⁶

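### Protocol 11.5 requires imaging confirmation of a palpation spleen response, but the protocol's own Stage 3A CMML criteria, which the SAP copies and counts, do not

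*Protocol*

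**What the plan says.** - **Protocol 11.5 (Physical Examination).** Spleen and liver are palpated on the schedules for Stage 2 (Tables 2 and 3) and Stage 3A (Tables 4 and 5). The section states that "a spleen response by palpation must be confirmed by imaging studies to show reduction in spleen volume", with liver volume substituted in splenectomized patients, and refers to Appendix 18. It gives no percentage threshold and no time window.
- **Protocol 11.12** assigns the criteria: Table 6 for MF, Table 7 for CMML in Stage 2, Table 8 for CMML in Stage 3A.
- **Protocol Table 6 (MF)** has the imaging condition: "A spleen response requires confirmation by MRI or CT showing" a volume reduction of at least 35%.
- **Protocol Table 8 (CMML, Stage 3A)** does not. It asks for "Either a minimum 50% reduction in palpable splenomegaly of a spleen that is at least 10 cm at baseline", or for a spleen felt at more than 5 cm to become impalpable. SAP Table 8-4 has the same text. The only verification there is persistence: "response must be verified at" 8 weeks or later.
- **SAP 4.3.1** says that for CMML "the number and percentage of patients who achieved erythroid, platelet, neutrophil, spleen or symptoms responses will also be presented", using SAP Section 8.2, and adds time to each response. **SAP 4.3.2** adds "the median duration of response for each category of clinical benefit, including erythroid, platelet, neutrophil, spleen or symptoms responses".
- **Imaging.** Stage 3A patients have MRI or CT at baseline, at the end of Cycles 1 and 4, and then every 12 weeks. The schedule footnote says: "Scan must include measurement of spleen and liver volume". SAP 4.3.5 says "Spleen size by MRI/CT will be summarized over time for all patients with baseline splenomegaly" and counts reductions of at least 10%, 25% and 35%, without linking them to the spleen-response definition.

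**The concern.** The protocol gives two rules for the same event. Under Section 11.5 a palpation response stands only if a scan shows a smaller spleen. Under Table 8, palpation and persistence are enough. The SAP analyses the second rule, and its Section 5 (changes to planned analyses) does not mention the first.

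The study is open-label, has no randomised comparator, and response is investigator-assessed. Palpation distance is a judgement made by someone who knows the treatment, so an imaging check is the natural guard against optimistic readings. Spleen response is also one of the MDS/MPN 2015 components that Stage 3A exists to evaluate (SAP 1.1.3.3 and 3.7), and on its own it can place a patient in the clinical-benefit category. As the plan stands, a reader of the study report could not tell whether a reported CMML spleen response had been confirmed.

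**Working it through.** This is mainly a comparison of texts, followed by a small calculation of size.

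1. **Does 11.5 reach Stage 3A CMML?** It cites the Stage 3A schedules and names no disease. Where Section 11 means MF only, it says so: the additional ECGs in 11.7 and urinalysis in 11.10. As written, 11.5 covers CMML.

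2. **What is in Appendix 18?** Table 6 (MF) carries the imaging condition. Table 7 (Stage 2 CMML) has no spleen category. Table 8 (Stage 3A CMML) has a spleen category with no imaging condition. So 11.5 sends the reader to a CMML definition that lacks the confirmation it requires.

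3. **What does the SAP count?** SAP 4.3.1 points to Section 8.2. Table 8-3 there has no spleen category, so Table 8-4 is the only CMML definition available, and it is palpation-only. SAP 4.3.2 derives duration from the same categories.

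4. **Is confirmation imposed elsewhere?** SAP 4.3.5 and 4.3.7 summarise MRI/CT measurements, but neither conditions the spleen-response count on them. SAP 3.5 describes the CMML response data as investigator-reported. Nothing in the analysed criteria requires or checks a scan.

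5. **The plan's own figure.** The Stage 3A sample-size sections state an 80% chance of at least one responder among 10 patients at a true rate of 0.15. Check: 1 − 0.85^10 = 1 − 0.197 = 0.803, which agrees. That response is a fall in spleen volume linked to symptom score, not the palpation category, so this point leaves the figure unchanged.

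6. **Size of one reclassification.** SAP 3.10 takes percentages from the total population.
   - Planned cohort of about 20: 1/20 = 5 percentage points.
   - Both cohorts together, about 40: 1/40 = 2.5 points.
   - Only if the rate were shown among the 8–10 splenomegaly patients planned per cohort: 1/10 = 10 to 1/8 = 12.5 points.

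   SAP Section 5 says Stage 3A enrolment was not continued, so actual denominators may be smaller and the steps larger.

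7. **Timing of palpation and scans.** Palpation is scheduled at the end of every cycle. Scans fall at the end of Cycles 1 and 4 and then every 12 weeks, which is three 28-day cycles (3 × 28 = 84 days). The ends of Cycles 2, 3, 5 and 6 therefore have palpation but no planned scan. Imaging may also become less frequent in stable patients. Formal response assessments do share the scan schedule.

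**The case against.** The best defence is that the sentence in 11.5 was written for MF. Its provision for liver volume in splenectomized patients matches the footnotes to Table 6, and Table 8 has nothing similar. On that view the remedy is to limit 11.5 to MF. This is plausible, and the fix allows for it, but the documents do not say it.

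The finding also has limited weight. SAP 1.2.5.1 names objective response rate as the primary efficacy endpoint. The analyses are descriptive with no type I error control, and Stage 3B will not start. All of this is correct and keeps the point modest.

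Three stronger readings are tempting and should be resisted:

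- A reader might infer that the SAP departs from the protocol. It does not: Protocol 11.12 names Table 8 for Stage 3A, and the SAP reproduces its spleen criterion. The conflict lies inside the protocol and was carried over.
- A reader might infer that unconfirmed responses are in fact being counted. The documents show only that they can be. Investigators are bound by 11.5 and may have looked at a scan before reporting a response.
- A reader might infer that spleen volume is collected at every palpation and then ignored. Neither half holds: scans are less frequent than palpation, and SAP 4.3.5 and 4.3.7 report the imaging results in their own right. What is missing is the link to the spleen-response count.

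**Conclusion.** The point holds as an internal contradiction in the protocol that the SAP resolves, without saying so, in favour of the rule that lacks the safeguard. It bears on the CMML spleen-response rate, time to response and duration, and on the clinical-benefit category. The objective response rate counts CR and PR and does not use the spleen-response category. MF already has its own imaging rule.

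The working size is about 5 percentage points per reclassified patient. This assumes the planned cohort of 20 and the total-population denominator. A reader might prefer 10–12.5 points, but the 8–10 patient subset belongs to the volume-based sample-size response, and SAP 4.3.1 names no splenomegaly-only denominator for the palpation category. How many patients would be reclassified cannot be derived, because the documents give no rate at which scans confirm palpation.

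A reader might also infer that 35% is the required cut for CMML. It is a response condition only in the MF criteria; Section 11.5 asks for a reduction without stating how much.

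**What to change.** Reconcile Protocol 11.5 with Protocol Table 8 and SAP Table 8-4, and record the outcome in SAP Section 5.

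- **In SAP 4.3.1 and 4.3.2,** report a CMML spleen response as imaging-confirmed when the MRI or CT at the matching formal response assessment, or the nearest scheduled scan within a stated window, shows a reduction in spleen volume from baseline.
- **Threshold.** Show the 35% cut from SAP 4.3.5 as a display only, since 11.5 sets no threshold for CMML.
- **Unconfirmed responses.** List separately the palpation responses that the scan does not confirm and those with no scan in the window.
- **If 11.5 was intended for MF only,** limit it to MF, label the CMML endpoint as palpation-based, and still show the imaging-confirmed count beside it.

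The cost is SAP wording and a small derivation from volumes already collected; no new scans are needed. The downside is that some palpation responses arising between scans will be dated later or classed as unconfirmed, which affects time to response and duration as well as the rate.
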